#### 13. SPECIMEN BANKING

- If specimens will be banked for future research, describe where the specimens will be stored, how long they will be stored, how they will be accessed and who will have access to the specimens
- List the information that will be stored with each specimen, including how specimens are labeled/coded
- Describe the procedures to release the specimens, including: the process to request release, approvals required for release, who can obtain the specimens, and the information to be provided with the specimens.

No specimens will be banked.

#### 14. DATA MANAGEMENT AND CONFIDENTIALITY

- Describe the data and specimens to be sent out or received. As applicable, describe:
  - What information will be included in that data or associated with the specimens?
  - Where and how data and specimens will be stored?
  - How long the data will be stored?
  - Who will have access to the data?
  - Who is responsible for receipt or transmission of data and specimens?

Version Date:7/26/2017 Page 9 of 19

• Describe the steps that will be taken to secure the data during storage, use and transmission.

## Plan for Data Management:

The PI will be responsible for the collection and storage of study data. The research coordinator will assign and record the Subject IDs on the Coded Identifier List. The hardcopy study eligibility forms and data collection forms will be kept in separate, locked file cabinets in the research office. The data elements from the data collection forms and imaging studies will be recorded in REDCap. The ultrasound images from the sonoHSG will be stored in the research PACS. A research report will be issued and kept as part of the research records. This report will be available to the fertility clinicians to incorporate into their clinical report of the HSG but will not be available in the clinical PACS. Study data in these files will be analyzed by our study statistician(s) on computers that will be protected by passwords and active anti-virus software. Laptops, USB flash drives, and/or external hard drives used for data analysis purposes by our study staff will be protected by password, active anti-virus software, and encryption by Northwell standards. Our data analysts do not have access to the link between the study Subject IDs and patient names.

The PI and Co-Investigators are responsible for ensuring proper study documentation to verify compliance with IRB and GCP guidelines. As part of the safety plan for this study, the study staff will review study patient records to ensure that appropriate mechanisms to protect the safety of study participants are being followed, that protocol requirements are being adhered to, and that data are accurate, complete, and secure. Patient records include consent forms, data collection forms, and/or adverse event logs, and medical charts.

At periodic meetings of the study staff, the PI will report on the number of subjects enrolled in the study.

The coordinator will work with study personnel to securely store and record all study data. Only investigators who are listed on the IRB will have access to PHI associated with the study. All study documents will be stored securely on an IRB and HIPAA compliant system, and paper documents will be stored in a locked office.

#### 15. DATA AND SAFETY MONITORING PLAN

A specific data and safety monitoring plan is only required for greater than minimal risk research. For guidance on creating this plan, please see the Guidance Document on the HRPP website.

Part I – this part should be completed for all studies that require a DSMP.

Part II – This part should be completed when your study needs a Data and Safety Monitoring Board or Committee (DSMB/C) as part of your Data and Safety Monitoring Plan.

### Part I: Elements of the Data and Safety Monitoring Plan

- *Indicate who will perform the data and safety monitoring for this study.*
- Justify your choice of monitor, in terms of assessed risk to the research subject's health and well being. In studies where the monitor is independent of the study staff, indicate the individual's credentials, relationship to the PI, and rationale for selection
- List the specific items that will be monitored for safety (e.g. adverse events, protocol compliance, etc)
- Indicate the frequency at which accumulated safety and data information (items listed in # above) will be reviewed by the monitor (s) or the DSMB/C.
- Where applicable, describe rules which will guide interruption or alteration of the study design.
- Where applicable, indicate dose selection procedures that will be used to minimize toxicity.
- Should a temporary or permanent suspension of your study occur, in addition to the IRB, indicate to whom will you report the occurrence.

The study monitoring will consist of the principal investigator serving as the study's safety monitor. The principal investigator will review the aggregate study data after the first 10 subjects are enrolled and have completed follow-up. The principal investigator will also review the aggregate study data at least annually, starting from the first enrolled subject, until the completion of enrollment and all study follow-up procedures. During these reviews, the principal investigator will review the study data to determine if aspects of the study need to be changed or stopped. In addition, he will review any and all deviations, adverse events and unanticipated problems that may occur to determine their relatedness to the study, their severity, and whether they require study changes. In addition, any unanticipated problems or instances of noncompliance will be reported to the IRB as per their reporting requirements. If any protocol changes are needed, an investigator will submit a modification request to the IRB. Protocol changes will not be implemented prior to IRB approval unless necessary to eliminate apparent immediate hazards to the research subjects. In such a case, the IRB will be promptly informed of the change following implementation.

#### Part II: Data and Safety Monitoring Board or Committee

- When appropriate, attach a description of the DSMB.
- Provide the number of members and area of professional expertise.
- Provide confirmation that the members of the board are all independent of the study.

No data and safety monitoring board or committee is appointed because the study procedures are standard of care bearing minimum risk.

#### 16. WITHDRAWAL OF SUBJECTS

- Describe anticipated circumstances under which subjects will be withdrawn from the research without their consent
- Describe procedures for orderly termination

• Describe procedures that will be followed when subjects withdraw from the research, including partial withdrawal from procedures with continued data collection.

The study can be discontinued by the study investigators at any time. Such discontinuation will have no effect on standard patient care.

Subjects can withdraw from the study at any time.

Subjects may be excluded from study analyses due to missing data for one or more of the following reasons:

- Failure to complete both study procedures in the specified time period.
- Failure to complete the pain scale survey.

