#### The specific goals are:

- To demonstrate the utility of sonoHSG as a first line imaging examination in the workup of infertility.
- To streamline the workup of infertility by diagnosing tubal pathology at the time of sonohysterogram.
- To make the workup of infertility safer.
- To improve patient comfort.
- To assess the side effects and complications of and difficulties related to the procedure.
- To assess patient tolerance by using the Pain Scale.

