#### Secondary Endpoint:

- Quantification of level of patient pain in regard to sonoHSG versus HSG

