#### 11. RESEARCH PROCEDURES

- *Include a detailed description of all procedures to be performed on the research subject and the schedule for each procedure.*
- *Include any screening procedures for eligibility and/or baseline diagnostic tests*

- Include procedures being performed to monitor subjects for safety or minimize risks
- *Include information about drug washout periods*
- If drugs or biologics are being administered provide information on dosing and route of administration
- Clearly indicate which procedures are only being conducted for research purposes.
- If any specimens will be used for this research, explain whether they are being collected specifically for research purposes.
- Describe any source records that will be used to collect data about subjects
- Indicate the data to be collected, including long term follow-up

Patients will be presented with the study information at the point of contact at the fertility clinic. They will then be contacted via phone prior to their scheduled appointment. A detailed overview of the study will be presented as well as the consent form. Upon verbal agreement over the phone, the clinician and/or study coordinator will go over the consent process in person on the day of the scheduled visit. As part of this study, subjects will have both the HSG and SonoHSG performed consecutively. The HSG will be performed as part of standard of care and the sonoHSG will be performed as part of research. In order to reduce bias, the procedures will be randomized in REDCap before each subject's scheduled visit. The clinicians will be blinded to the results of each procedure until both procedures have been completed.

The pain scale will be administered verbally immediately after each procedure by the technician/other study personnel in the procedure room.

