#### 12. STATISTICAL ANALYSIS

- *Describe how your data will be used to test the hypotheses.*
- State clearly what variables will be tested and what statistical tests will be used.
- *Include sample size calculations.*
- If this is a pilot study, state which variables will be examined for hypothesis generation in later studies.

Standard methods for descriptive statistics will be used, such as means, medians, proportions, and their associated 95% confidence intervals.

Concordance of the results between sonoHSG and HSG will be calculated using Gwet's Agreement Coefficient (AC1). An AC1 of  $\geq$ = 0.80 will be considered successful concordance between the two measures.

A repeated measures analysis of variance (RM-ANOVA) model will be used to examine the effect of treatment (sonoHSG vs. HSG) on the pain measure. The model will include the order in which the treatments are performed and the interaction between order and treatment. If the interaction is not found to be significant, only the main effects of treatment and order will be analyzed.

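### Section 16 allows a woman who does not complete both procedures to be left out of the pain comparison even when her pain scores were recorded

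*Protocol*

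**What the plan says.** Section 16 (Withdrawal of Subjects) sets the rule: "Subjects may be excluded from study analyses due to missing data for one or more of the following reasons". Two reasons follow:

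- "Failure to complete both study procedures in the specified time period"
- "Failure to complete the pain scale survey"

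The rule is not tied to a particular endpoint, and it does not separate stopping for pain from other causes. Section 16 does not define the time period it refers to. It also does not answer the template's own prompt about women who withdraw from part of the procedures while data collection continues.

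Four other places bear on this:

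- Section 11 (Research Procedures), on timing: "The pain scale will be administered verbally immediately after each procedure by the technician/other study personnel in the procedure room".
- Section 10, the secondary endpoint: "Quantification of level of patient pain in regard to sonoHSG versus HSG".
- Section 4, one of the specific goals: "To assess patient tolerance by using the Pain Scale".
- Section 12: "A repeated measures analysis of variance (RM-ANOVA) model will be used to examine the effect of treatment (sonoHSG vs. HSG) on the pain measure". Its terms are treatment, order and their interaction. Nothing is said about women with only one score.

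**The concern.** Each woman has two examinations in succession, and the protocol's background in section 3 describes HSG as causing significant discomfort. It is foreseeable, though the protocol does not say so, that some women will decline the second procedure after a painful first one, or that an examination will be cut short. Such a woman has not completed both procedures and may be excluded under the first reason, whatever pain data she has given.

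The exclusion would then depend on something plausibly caused by the outcome being compared. The scores most likely to be lost are high ones, and they are the most informative about tolerance. The rule is also discretionary, with no criterion for when it is used, so it could be applied after the scores are known. With about 30 women, two or three exclusions are a noticeable share of the data.

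**Working it through.** **Step 1. Reading sections 11 and 16 together.**

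| Situation | Pain scores under section 11 | Section 16, reason 1 |
|---|---|---|
| First procedure completed, second declined | One, for the first procedure | Applies |
| Both started, one cut short, scale given after each | Two | Applies |
| Both completed, a survey not answered | One or none | Does not apply; reason 2 does |

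In the second row no pain score is missing, yet the woman may still be excluded. Section 11 does not say expressly that the scale is given when an examination is cut short, so that row depends on practice. The first row does not.

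**Step 2. Inputs for the size.** The protocol gives 30 women (up to 50). It gives no stopping rate, pain SD, expected difference or within-woman correlation, and does not state the range of the scale. There is no protocol figure to reproduce, and everything below is assumed, on a 0-10 scale with SD 2.5.

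**Step 3. Leaving after a very painful first procedure of either kind.** HSG mean 5.5, sonoHSG mean 4.0, correlation 0.5, scores rounded and kept within 0-10. Half of the women scoring 8 or more on the first procedure leave. In simulation:

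- HSG mean: 5.47 in all women, 5.24 after exclusion.
- Difference: 1.43 in all women, 1.38 after exclusion, a shift of 0.05.

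**Step 4. Either procedure stopped, with a chance that rises with its own score.** There were 18 scenarios: worse procedure with mean 6, the other 5 or 4, correlation 0.3 to 0.7, and about 6% to 14% of the worse procedure's examinations stopped.

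| | All women | After exclusion |
|---|---|---|
| Mean, worse procedure | 5.95 | 5.35 to 5.73 |
| Difference, smaller effect | 0.95 | 0.85 to 0.93 |
| Difference, larger effect | 1.90 | 1.72 to 1.87 |

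The worse procedure's mean falls by 0.2 to 0.6 points. The milder procedure's mean falls too, because scores are correlated and some of its own examinations are stopped. The net shrinkage of the difference is about 2% to 11%, or 0.02 to 0.18 points.

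**Step 5. Only one procedure stopped.** With the inputs of step 3 and half of scores of 8 or more stopped:

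- HSG only (10.5% of women): 1.43 becomes 1.23, a shift of 0.20 against sonoHSG.
- sonoHSG only (4.0% of women): 1.43 becomes 1.53, a shift of 0.10 in favour of sonoHSG.

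**Step 6. A constructed case with 30 women.** Twenty-seven average 4.0 (sonoHSG) and 5.5 (HSG). In three, sonoHSG is stopped at 9 and HSG scores 6.

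- sonoHSG: (27 × 4.0 + 3 × 9)/30 = 135/30 = 4.50
- HSG: (27 × 5.5 + 3 × 6)/30 = 166.5/30 = 5.55
- Difference with all women: 5.55 − 4.50 = 1.05
- Difference in completers: 5.5 − 4.0 = 1.50, an overstatement of 0.45

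**Step 7. Yardstick.** With SD 2.5 and correlation 0.5, the SD of the paired difference is √(2 × 6.25 × 0.5) = 2.5. Its standard error with 30 women is 2.5/√30 = 0.46. The 0.05 of step 3 is about a tenth of that; the 0.45 of step 6 is about one standard error.

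**Step 8. After the change.** A linear mixed model fitted to all observed scores under the step 3 mechanism (8,000 simulated women) gave 1.43 against a true 1.43. In step 6 every woman has both scores, so an ordinary paired analysis of all 30 already gives 1.05.

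**The case against.** The strongest reply is that section 16 permits exclusion rather than requiring it, and ties it to missing data. The two reasons can be read as matching the two endpoints: incomplete procedures leave concordance without data, and an incomplete survey leaves pain without data. On that reading a woman with pain scores is never dropped from the pain analysis. The reading is reasonable, but section 16 does not say it. The rule refers to study analyses in general.

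A reader might infer that section 12 itself discards incomplete pairs. That is how a classical repeated measures ANOVA usually behaves, but section 12 does not say so, and the handling of incomplete pairs is commonly left to the SAP. This part of the objection stands: section 12 is not in error here. The exclusion in section 16 is different, because the protocol itself states it.

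It is also true that no passage reports that examinations are stopped for pain, or how often. Section 17 describes discomfort as a rare risk of ultrasound examinations. Section 4 includes difficulties related to the procedure among the goals, and section 15 has deviations and adverse events reviewed, so abandoned examinations may come to notice. None of this places their scores in the pain comparison.

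Finally, the study is a feasibility pilot and pain is secondary. That limits the importance of the point but does not remove it.

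**Conclusion.** The point holds as a weakness in a stated rule. Section 16 permits a woman with recorded pain scores to be left out of the pain comparison for a reason that may be related to pain. Where it is, the exclusion can understate pain for the procedure stopped more often.

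The documents do not support the stronger conclusion that such scores are discarded, or that the pain result will be seriously biased. The exclusion is optional and no stopping rate is given. Under the assumed inputs the shift in the difference is about 0.05 points when women leave after a very painful first procedure of either kind. It is 0.02 to 0.18 when one pain-dependent rule governs stopping in both procedures. It is larger relative to the number stopped when stopping is one-sided, and the 0.45 is a constructed case, not an expectation.

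The direction depends on which procedure is stopped more. If it is HSG, the rule works against the advantage the protocol expects for sonoHSG; if sonoHSG, it flatters it. The change is worth making because it costs almost nothing and removes an outcome-related exclusion from the only secondary endpoint.

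**What to change.** - **Section 16.** Limit the first reason to the concordance analysis. State that every recorded pain score enters the pain analysis, including one taken when an examination is stopped early.
- **Section 11.** Say that the pain scale is also given when an examination is stopped early, so that this score exists by design.
- **Section 12.** Fit the treatment and order effects with a model that uses all observed scores, for example a linear mixed model with a random woman effect. This matters for women with only one score; for those with both it leaves the comparison essentially unchanged.
- **Reporting.** Give the number of each procedure not completed, with the reason.

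The cost is a few sentences and one data field for non-completion and its reason, with no added subjects or visits. The drawback is that a score from a stopped examination reflects a shorter exposure, so the completers-only result should be shown beside the main one.

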#### 17. RISKS TO SUBJECTS

- Describe any potential risks and discomforts to the subject (physical, psychological, social, legal, or other) and assess their likelihood and seriousness and whether side effects are reversible. Where appropriate, describe alternative treatments and procedures that might be advantageous to the subjects.
- *Include risks to others , like sexual partners (if appropriate)*
- Discuss why the risks to subjects are reasonable in relation to the anticipated benefits and in relation to the importance of the knowledge that may reasonably be expected to result.
- Describe the procedures for protecting against or minimizing any potential risks, including risks to confidentiality, and assess their likely effectiveness.

#### Physical Risks:

The study bears minimal risk as ultrasound exams are generally low risk as they are free of radiation. Some risks, although rare, may involve the following:

- Discomfort
- Skin irritation
- Bruising

Risks of the sonoHSG, although rare, may involve the following:

- Infection of the uterus/pelvis
- Bleeding

#### Psychosocial/Legal Risks:

Several steps have been taken to minimize the loss of confidentiality and privacy with the data collected during this research.

All study records will be organized in files and stored in the PI's locked office. Data will be compiled using a data collection form developed for the study. Results will

also be stored on the PI's computer that is password-protected. Electronic backup files will be stored on a password-protected external drive that will be locked in the PI's office. The research images will be kept in the research PACS. Only the PI and co-investigators will have access to printed and electronic records. If the study results are published, no Protected Health Information (PHI) will be published. The confidentiality of the patient will be preserved under all circumstances.

To minimize the breach of confidentiality risk, we will not use the subject's name or medical record number in any study records. Instead, a unique Subject ID will be assigned to each subject. Only these numbers will be used on study documents that relate to the subject. We will keep the hardcopy Coded Identifier List of subject names and corresponding Subject IDs in a locked file cabinet separate from the hardcopy data collection forms, which are coded only with the Subject ID and also secured in locked storage cabinets in the PI's office.

#### 18. RESEARCH RELATED HARM/INJURY

- Describe the availability of medical or psychological resources that subjects might need as a result of anticipated problems that may be known to be associated with the research.
- If the research is greater than minimal risk, explain any medical treatments that are available if research-related injury occurs, who will provide it, what will be provided, and who will pay for it.

If the subject is injured as a result of being in the study, they will receive medical care and treatment as needed from Northwell Health. However, the subject will be responsible for the costs of such medical treatment, directly or through their medical insurance or other forms of medical coverage. There is no payment available through the grant or the institution.

#### 19. POTENTIAL BENEFIT TO SUBJECTS

- Explain what benefits might be derived from participation in the study, noting in particular the benefit over standard treatment (e.g. a once-a-day administration instead of four times a day, an oral formulation over an IV administration).
- Also state if there are no known benefits to subjects, but detail the value of knowledge to be gained

Fertility patients comprise a unique and special group. Women in pursuit of having a child, a family, are often times anxious, nervous and frequently depressed. Navigating the fertility maze may seem cumbersome and overwhelming. This new procedure promises to remove one big, painful hurdle (HSG) almost every infertile

woman encounters, and allow a happier and faster road to motherhood. This initiative represents major collaboration between Northwell Health Fertility and Radiology and will streamline the diagnosis and treatment of infertility while providing a safer and less painful first line imaging examination for the study participants. The knowledge gained from this study will help to standardize sonohysterosalpingogram in the work up of infertility.

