# 3. INTRODUCTION/BACKGROUND MATERIAL/PRELIMINARY STUDIES AND SIGNIFICANCE

- Describe and provide the results of previous work by yourself or others, including animal studies, laboratory studies, pilot studies, pre-clinical and/or clinical studies involving the compound or device to be studied.
- Include information as to why you are conducting the study and how the study differs from what has been previously researched, including what the knowledge gaps are.
- Describe the importance of the knowledge expected to result

Recently, studies have shown that the sonoHSG alone is as reliable as the traditional HSG for evaluating fallopian tube patency, with the benefits of eliminating radiation exposure and the use of potentially harmful iodinated contrast. SonoHSG is also less painful when compared to the HSG and by reducing the number of procedures from two to one, the risk of infection is reduced. Additionally, a single procedure will help to shorten the diagnostic process of infertility and expedite treatment. Indeed, several recent reports support the use of sonoHSG as a first line diagnostic test for the workup of infertility. Ultimately, this test will be safer, more comfortable, and less expensive for our patients. SonoHSG is a long sought for alternative for tubal patency in place of the old, yet still practiced, "gold standard" HSG. We believe this initiative will help our institution streamline time to treatment and diagnosis of tubal pathology while improving patient experience.

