#### Schedule of Events:

	Pre-Visit	Visit 1	Follow-Up Visit (1-3 weeks)
Recruit Subject	X	X	
Evaluate Eligibility	X	X	
Initiate Informed Consent	X	X	
Obtain Written Informed Consent		X	
Collect Demographic Information		X	

HSG and sonoHSG (order decided via randomization)	X	
Administer the Pain Scale Survey (following each procedure)	X	
Follow-up with subject via phone to assess any complications/infections		Х

The procedures that would account as being research are obtaining informed consent, administering the pain scale surveys, performing the sonoHSG and the follow-up phone call.

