#### 23. CONSENT PROCESS

*If obtaining consent for this study, describe:* 

- Who will be obtaining consent
- Where consent will be obtained
- Any waiting period available between informing the prospective participant and obtaining consent
- Steps that will be taken to assure the participants' understanding
- Any tools that will be utilized during the consent process
- Information about how the consent will be documented in writing. If using a standard consent form, indicate such.
- Procedures for maintaining informed consent.

A clinician and/or coordinator on the study will approach the prospective subject at the point of clinical care. If the subject is identified before their visit, study personnel may contact the subject via phone to discuss the protocol. The full written consent process will be done in person on the day of the first visit.

Study personnel will review every element of the consent, giving the subject time to ask questions. If the subject is amenable to enrollment after reviewing the consent, the subject will provide written documentation on the consent form.

In the state of NY, any participants under the age of 18 are considered children. If your study involves children, additional information should be provided to describe:

- How parental permission will be obtained
- From how many parents will parental permission be obtained
- Whether permission will be obtained from individuals other than parents, and if so, who will be allowed to provide permission. The process used to determine these individual's authority to consent for the child should be provided
- Whether or not assent will be obtained from the child
- How will assent be documented
- Whether child subjects may be expected to attain legal age to consent to the procedures for research prior to the completion of their participation in the research. If so, describe the process that will be used to obtain their legal consent to continue participation in the study. Indicate what will occur if consent is not obtained from the now-adult subjects.

If the study involves cognitively impaired adults, additional information should be provided to describe:

- The process to determine whether an individual is capable of consent
- Indicate who will make this assessment

- The plan should indicate that documentation of the determination and assessment will be placed in the medical record, when applicable, in addition to the research record.

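### Section 19 promises participants a less painful examination although each of them has both tests and the pain difference is the secondary endpoint; if that message reaches them, randomised order cannot remove the resulting expectation bias

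*Protocol*

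**What the plan says.** **The benefit.** Protocol section 19 (Potential Benefit to Subjects) describes HSG as a painful obstacle and says that the initiative is "providing a safer and less painful first line imaging examination for the study participants". Section 3 states the same belief as background, with citations: "SonoHSG is also less painful when compared to the HSG".

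**The endpoint.** The only secondary endpoint in section 10 is "Quantification of level of patient pain in regard to sonoHSG versus HSG".

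**The design.** Under section 11, "subjects will have both the HSG and SonoHSG performed consecutively". HSG is the standard-of-care test and sonoHSG is added for research (sections 11 and 21). Only the order is randomised (Schedule of Events).

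**The rating.** Section 11 has a technician or other study staff ask for the pain score aloud, in the procedure room, right after each test. The only blinding described is of clinicians, and only to the results of the procedures.

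**What patients hear beforehand.** In the phone contact described in section 11, "A detailed overview of the study will be presented as well as the consent form". On the visit day, according to section 23, "Study personnel will review every element of the consent, giving the subject time to ask questions". Neither section says how the expected pain of the two tests is to be described.

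**The analysis.** Section 12 plans an RM-ANOVA with treatment, order and their interaction; the interaction is dropped if not significant.

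**The concern.** There are two linked problems.

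First, the sentence in section 19 does not fit the study. A woman who joins has the HSG she would have had anyway, plus a second transcervical imaging procedure. Less pain may be a benefit to future patients if sonoHSG replaces HSG. It is not a benefit of taking part here. This holds whatever the consent form says.

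Second, the sentence announces the answer to the secondary question. Pain is a subjective rating, the patient knows which test she has just had, and she reports to study staff. If she has been told that sonoHSG is the gentler test, part of any difference may reflect what she was told. A pain advantage obtained that way would be hard to interpret, both for the change in practice that section 3 has in view and for the larger trial foreseen in section 8.

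**Working it through.** The protocol gives no SD, effect size, significance level or scale range for pain, and section 8 sets the sample size of 30 on feasibility, so there is no stated figure to reproduce. Two things can be checked: whether the planned analysis could remove an expectation effect, and how much a given effect would matter.

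**1. Does randomised order remove it?** Let the true pain difference be 0. Let *b* be the amount by which expectation lowers the sonoHSG score, and *p* the change in score from first to second procedure. The expected sonoHSG minus HSG difference is:

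- sonoHSG first: (−b) − p = −b − p
- HSG first: (−b + p) − 0 = −b + p

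The average of the two orders, which is the treatment effect, is [(−b − p) + (−b + p)]/2 = −b. The contrast between the orders is (−b − p) − (−b + p) = −2p, which does not contain *b*. So the order terms absorb *p* and leave *b* wholly inside the treatment effect, whether or not the interaction is kept.

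A simulation of this design (20,000 studies per setting, half of the women in each order) agrees. For b = 0.5, 1.0 and 1.5 the mean estimates were about −0.5, −1.0 and −1.5, both with p = 0 and with p = 1. With b = 0 and p = 1 the rate of significant results stayed at about 5%. Randomised order does its own job, but not this one.

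**2. How much would a given shift matter?** Assumptions that are not in the protocol: 0–10 scale, two-sided 5% test, no true difference, SD of the within-woman difference 2 or 3 points. From the protocol: n = 30 (section 8), with a cap of 50. The test statistic follows a non-central *t* with n − 2 degrees of freedom and non-centrality b/(SD/√n).

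For n = 30, SD/√n is 2/5.477 = 0.365 or 3/5.477 = 0.548. A shift of 0.5 gives non-centrality 0.5/0.365 = 1.37 or 0.5/0.548 = 0.91. A shift of 1.0 doubles these to 2.74 or 1.83.

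Chance of a significant pain difference:

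| Shift b | n = 30, SD 2 | n = 30, SD 3 | n = 50, SD 2 | n = 50, SD 3 |
|---|---|---|---|---|
| 0 | 5% | 5% | 5% | 5% |
| 0.5 | 26% | 14% | 41% | 21% |
| 1.0 | 75% | 42% | 93% | 64% |
| 1.5 | 98% | 75% | >99% | 93% |

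Enrolling up to the cap makes the problem worse, because a larger sample estimates the biased contrast more precisely.

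**The case against.** The strongest reply is that section 19 is not text for patients. It answers a form's prompt to the investigator, "Explain what benefits might be derived from participation in the study, noting in particular the benefit over standard treatment", and is written for the ethics board. A reader might infer that women are told that sonoHSG hurts less and that the pain comparison is therefore biased. The documents do not support that. The consent form and the content of the phone overview are not shown, and no section says that the section 19 wording is passed on. Nor do they show that the briefing comes only minutes before the rating: consent and both procedures fall on the same visit, but no interval is given. This part of the objection stands, and it makes the bias a conditional risk.

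The size and direction of any shift are also assumed. A woman promised less pain might be disappointed and score sonoHSG higher. A shift in favour of sonoHSG is the likelier direction, but it is not shown.

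It can also be said that pain is a secondary endpoint without a success threshold, in a feasibility pilot to be followed by a powered trial. That is true and limits the consequence.

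Finally, patients must be told the risks and discomforts of each test, and the protocol believes that these differ. A demand to describe both tests in identical terms could distort that disclosure, so none is made here. Neutral wording will also not erase views that a patient already holds about HSG.

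What the objection does not reach is the sentence itself. It promises study participants a benefit that the two-test design does not deliver, on the question that the study is meant to answer.

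**Conclusion.** The point holds in a conditional form. It is certain from the protocol that section 19 offers participants a less painful examination although each has both tests, and that it treats the secondary endpoint as settled. It is also certain that randomised order and the order terms cannot remove an expectation attached to one of the procedures.

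It is not established that the message reaches patients. If it does, the sonoHSG–HSG pain contrast is open to bias, probably in favour of sonoHSG, by an amount that the protocol gives no means of estimating. The illustrative false-positive rates at 30 women (14% to 26% for half a point, 42% to 75% for one point) rest on the assumed scale, SD, test level and shift. They show what such a shift would do; they are not an estimate of what will happen in this study. The concordance endpoint is unaffected.

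**What to change.** - **Section 19:** replace the sentence with one saying that subjects undergo both examinations, that whether one is less painful is what the study measures, and that no individual comfort benefit is promised.
- **Sections 11 and 23:** add that the risks and discomforts of each examination are disclosed in full, but that staff do not tell subjects which is expected to be less painful until both pain scores are recorded.
- **Consent form and phone overview:** check both for consistency with the new wording.

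The cost is an ordinary modification request to the IRB. The one downside is that the stated benefit becomes less attractive to potential recruits. The change has to be made in the conduct of the study, because no later analysis can separate an expectation effect from the treatment contrast.
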